5.8.3 EBV-associated Lymphoproliferative Disorder

The cumulative incidence of either EBV-associated lymphoproliferative disorder or EBV reactivation requiring therapy with rituximab will be described for each treatment arm using the Aalen-Johansen estimator, with death treated as a competing risk. Estimates and 95% CIs of the cumulative incidence of EBV-associated lymphoproliferative disorder/EBV reactivation will be provided at Day 180 post-randomization. The cumulative incidence of EBV-associated lymphoproliferative disorder/EBV reactivation will be compared between arms using Gray's test.

5.8.4 Evolution of Cell Populations

The evolution of specific cell populations over the 180-day follow-up period will be evaluated using samples obtained from approximately 50 participants (25 T-Guard and 25 ruxolitinib participants) at Days 0, 14, 28, 90 and 180 post-randomization. Specimens will either be collected and stored as viably frozen PBMCs to allow for phenotypic and functional analysis of specific cell subsets or collected in CytoChex blood preservation tubes for FCM analysis.

The following cell populations, amongst others, will be measured by flow cytometry analysis: Inflammatory Monocytes & Dendritic Cells, Recent Thymic Emigrants, CD4+, CD8+ Naïve & Memory Cells, CD4+ T Regulatory Cells, NK Cells, $\gamma\delta$ T Cells, and B cells.

The level of each cell population will be summarized for each arm using descriptive statistics at each assessment time considered. Changes in levels from baseline to each follow-up assessment time will be evaluated by arm using Wilcoxon signed rank tests. For the PBMC subsets collected from both arms, Wilcoxon rank sum tests will compare the changes between arms at each follow-up time point.

5.8.5 GVHD-related Biomarkers

Using the biomarker risk model from Major-Monfried, Renteria et al. 2018, the serum levels of GVHD-related biomarkers including REG3 α and ST2 and the 3-IS urine levels at enrollment and Day 6, 14, and 28 post-randomization will be used to estimate NRM probabilities for each participant at Day 180 following each assessment time point. The proportions of participants with high risk (defined as an estimated NRM greater than 0.29) will be described at each assessment time by treatment arm.

Moreover, the proportions of participants within each treatment arm experiencing a Day 28 CR will be described separately for participants with high risk vs. not at enrollment within each treatment arm using sample proportions and 95% Wilson score or Clopper-Pearson CIs, as appropriate. A logistic regression model will evaluate the prognostic value of biomarker risk (high vs. not) on the chance of attaining a Day 28 CR while adjusting for treatment arm.

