1.3.1.2.2 T-Guard Single-arm, Phase 1/2 Clinical trial in second-line SR-aGVHD Patients

Following the promising results of T-Guard for the indication SR-aGVHD in the investigator-initiated dose escalation study, a Phase 1/2 study XEN/TG-001 was conducted (Groth, van Groningen et al. 2018). The study was designed to evaluate the safety and efficacy of T-Guard in treating SR-aGVHD patients who were refractory to first-line therapy. In total 20 patients were treated with T-Guard with a dose of 4 mg/m² every other day x 4 doses. All patients had grade II to IV SR-aGVHD. Seventeen of these patients (85%) had grade III-IV SR-aGVHD, and all 20 patients had visceral involvement; 18 with GI (90%) and 5 with liver (25%) involvement. Sixteen patients (80%) had 2 or more organs involved. A validated two biomarker algorithm classified the majority of patients (11/20) as high-risk.

The Day 28 ORR (primary endpoint), defined as having a CR or PR without the need for initiation of other treatments due to insufficient response, was 60%. Day 28 CR was 50% and PR 10%. The Day 180 OS was 60%. The outcomes achieved were very favorable compared with the historical standard of care (SoC) data at the participating centers (Day 28 CR less than 20% and Day 180 OS 29%).

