3.5.1.5 GVHD-related Biomarkers

GVHD-related biomarker concentrations including serum Interleukin 1 receptor-like 1 (ST2) and Regenerating Family Member 3 Alpha (REG3α) concentrations and urine 3-Indoxyl Sulfate (3-IS) concentrations at baseline and at Day 6, 14, and 28 post-randomization will be used to estimate the probability of NRM at Day 180 post-assessment for each participant, using the NRM risk model from (Major-Monfried, Renteria et al. 2018). The proportion of participants with high-risk biomarker status (defined as estimated NRM greater than 0.29) will be described at each time point.

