5 STATISTICAL CONSIDERATIONS

5.1 STUDY DESIGN AND OBJECTIVE

This trial is a randomized, open-label, multi-center Phase 3 study designed to compare the efficacy and safety of T-Guard to ruxolitinib treatment of participants with Grade III-IV SR-aGVHD. A total of 246 participants will be enrolled from approximately 75 transplant centers in the US and Europe. All participants will be followed at minimum through Day 180 post-randomization.

The study will begin with a safety run-in phase of 24 randomized participants (12 to each arm), after which the remaining participants will be enrolled provided that safety concerns do not arise during the run-in.

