5.1.2 Randomization and Blinding

Participants will be randomized at the time of enrollment in a 1:1 ratio to the treatment arms. Randomization will be stratified by center region (US vs. Europe) and age group (at least 55 years vs. under 55). Stratified treatment assignments will be generated using permuted blocks of random sizes.

As this is an open-label trial, no blinding will be performed.

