5.8 ANALYSIS OF EXPLORATORY ENDPOINTS

The analysis of exploratory endpoints will be based on the ITT analysis population.

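### The biomarker model in Section 5.8.5 tests prognostic value only as above or not above 0.29; a model on the continuous score already planned should be added beside it

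*Combined protocol and SAP*

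**What the plan says.** Section 5.8.5 takes serum REG3α and ST2 and urine 3-IS at enrollment and Days 6, 14 and 28. Through a published risk model, these "will be used to estimate NRM probabilities for each participant at Day 180 following each assessment time point". The estimate is then cut: "The proportions of participants with high risk (defined as an estimated NRM greater than 0.29") are described by arm at each time. Section 3.5.1.5 uses the same cut: "The proportion of participants with high-risk biomarker status (defined as estimated NRM greater than 0.29) will be described at each time point".

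Day 28 CR is to be described by risk group at enrollment. One model follows: "A logistic regression model will evaluate the prognostic value of biomarker risk (high vs. not) on the chance of attaining a Day 28 CR", adjusted for treatment arm. That sentence does not itself name a time point, although the sentence before it concerns enrollment status. No model with the continuous estimate is planned.

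The analysis is exploratory, and Section 5.8 states: "The analysis of exploratory endpoints will be based on the ITT analysis population". Sections 3.5.1.5 and 5.8.5 give no effect size, alpha, power or expected share above 0.29, and no rule for missing biomarker samples in this analysis.

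**The concern.** The plan computes a graded risk estimate and then treats a participant just above 0.29 and one far above it as identical. The threshold is defined on NRM, whereas the model's outcome is Day 28 CR. The documents give no reason why the odds of CR should be flat on each side of that value and jump at it.

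If the relation is smooth, the binary term is a noisy stand-in for the score. A result showing no association could then come from the cut and not from a lack of prognostic value, and the plan has no second model to tell the two apart. A continuous model chosen after seeing the data would be a post hoc choice.

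**Working it through.** **Plan's own figure.** The documents state no power for the biomarker model. The nearest stated figure is for the primary comparison: 80.56% cumulative power in Table 5-2. A group-sequential simulation with the stated boundaries (Z of 2.6562 and 1.9817), futility at 4 or fewer CRs in 23, and CR rates of 43% and 26% gave 34.1% at the interim (stated 34.14%) and 80.4% cumulative. The trial-level inputs below are therefore read correctly.

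**Inputs from the documents**
- N = 246, from Section 5.1: "A total of 246 participants will be enrolled from approximately 75 transplant centers in the US and Europe".
- 123 per arm, from Section 5.1.2: "Participants will be randomized at the time of enrollment in a 1:1 ratio to the treatment arms".
- CR rates of 43% and 26% (Section 5.1.5).

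**Inputs assumed**
- A normally distributed score, linear on the logit of CR, with log-odds slope b per SD.
- A two-sided 5% Wald test.
- A share f above the cut. The base case is 55%, borrowed from the Phase 1/2 study in Section 1.3.1.2.2, where an algorithm "classified the majority of patients (11/20) as high-risk". That section does not say the algorithm used 0.29, so f is varied from 20% to 80%.

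**Information kept by the cut.** Relative efficiency is RE = φ(c)² / [f(1 − f)], where c is the normal quantile at 1 − f.
- f = 55%: c = −0.1257, φ(c) = 0.3958, RE = 0.1567 / 0.2475 = 0.633. About 37% is lost.
- f = 50%: RE = 0.637.
- f = 30%: RE = 0.576.
- f = 20% or 80%: RE = 0.490.

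A near-even split is where a cut of a normal score costs least.

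**Power under a smooth effect.** The information per unit of score variance is 246 × (0.43 × 0.57 + 0.26 × 0.74) / 2 = 53.8, with square root 7.336. The continuous model has non-centrality 7.336 × b. The binary model has that times √RE, which is √0.633 = 0.796. Power is Φ(non-centrality − 1.96). At f = 55%:

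| b per SD | Continuous, formula | Binary, formula | Loss | Simulation |
|---|---|---|---|---|
| 0.1 | 11.0% | 8.4% | 2.6 | loss about 3 |
| 0.3 | 59.5% | 41.7% | 17.8 | 59% vs 41% |
| 0.4 | 83.5% | 64.6% | 18.9 | 83% vs 65% |
| 0.5 | 95.6% | 83.1% | 12.5 | 95% vs 82% |
| 0.9 | 100% | 100% | 0 | loss near 0 |

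The simulated losses at b = 0.3, 0.4 and 0.5 are 18, 18 and 13 points. A separate set of runs gave 82.0% vs 63.5% at 0.4 and 95.1% vs 81.4% at 0.5.

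**Other shares.** Where the continuous model has 80% power, the binary model has 60.6% at f = 55%, 56.6% at 30%, and 50% at 20% or 80%. The losses are 19, 23 and 30 points.

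**Power if risk steps at the cut.** The roles reverse with the same RE. For a step in log odds of 0.8 at f = 55%, the binary model has non-centrality 0.8 × √(53.8 × 0.2475) = 2.92 and power 83%. The linear score has 2.92 × 0.796 = 2.32 and power 64%. Simulations over several step sizes and shares of 40%, 55% and 70% gave the binary model 2 to 22 points more power.

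**The case against.** The strongest reply is that the plan answers the question it poses. It evaluates a risk category at a pre-specified threshold tied to a cited risk model. The cut is not chosen from trial data, so there is no cut-point search and no inflation of type I error. Section 5.8.8 dichotomises EASIX in the same way. The endpoint is exploratory, and no alpha, stopping rule or treatment decision depends on it.

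Most of this stands. It shows that the binary model is legitimate and should stay. It does not show that the binary model is sufficient. Section 5.8.8 says its purpose is to validate risk categories, whereas Section 5.8.5 states no such purpose and asks about prognostic value.

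A second objection also stands: the power calculation for a smooth effect generates data from the very model it favours. The sign reverses under a step, so replacing the binary model with a linear one would exchange one untested shape for another.

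A reader might also infer from the 11/20 figure that 0.29 is close to a median split in this trial. The documents do not support that. The algorithm in Section 1.3.1.2.2 used two biomarkers and is not stated to use 0.29, while Section 5.8.5 also lists urine 3-IS. That study included Grade II disease (17 of 20 were Grade III-IV). The exact 95% interval for 11/20 is 32% to 77%.

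**Conclusion.** The point holds as a low-severity improvement. Section 5.8.5 plans a continuous estimate and tests its prognostic value for Day 28 CR only in two groups. If the relation is smooth, about 37% of the information is lost at a near-even split and more at an uneven one.

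A reader might take 13 to 18 points as the power this plan gives up. The documents do not establish that. The figure rests on 246 complete enrollment scores, a normal score, a logit-linear effect of 0.3 to 0.5 per SD, 55% high-risk and a two-sided 5% test. Across other slopes and shares the loss is about 0 to 30 points, and it becomes a gain for the binary model if risk steps at 0.29. Nor do the documents support calling the planned model invalid or biased. The primary analysis and its error control are unaffected.

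**What to change.** In Section 5.8.5, keep the planned logistic model with high vs. not. Pre-specify beside it a logistic model of Day 28 CR on the logit of the enrollment estimated NRM probability as a continuous term, adjusted for treatment arm. The term may be linear, or a spline to check shape. State in the same sentence that both models use the enrollment value. Leave the descriptive tables at 0.29 as they are.

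The cost is one or two sentences of analysis-plan wording and one extra model. The estimate is already planned, so no new samples, visits or data are needed.

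Having both models in advance covers a smooth and a step-shaped relation without a choice made after seeing the data.

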T-Guard Participants Only	Peripheral Blood¹ (SST Clot Tube) 5 mL Serum Pharmacokinetic Testing (2 aliquots) Cytokines testing during safety run-in and for patients experiencing an infusion reaction (1 aliquot) Free-RTA + free-mAb testing on selected left-over PK samples (1 aliquot)	Day 0 (1st infusion) Prior to study drug infusion and 4, 5, 6, 8, and 24 hours after start of infusion Days 2 & 4 (2nd & 3rd infusions) Prior to study drug infusion and 4 and 24 hours after start of infusion Day 6 (4th infusion) Prior to study drug infusion and 4, 6, 24, and 48 hours after start of infusion Notably no PK sampling is required on Weekend Days	Collect the blood sample and place into an SST Vacutainer tube containing clot activator. Allow blood samples to clot upright for 30-60 minutes in a tube rack prior to centrifugation, serum removal, and serum aliquot equally in 4 aliquots of 0.5 mL; storage at -80°C.	Frozen serum aliquots will be periodically batched-shipped to the BMT CTN Biorepository (US) or Ardena (Europe). One aliquot will be shipped from BMT CTN/Ardena to MyriadRBM for cytokine testing for the first 12 T-Guard patients, and in cases where patients experience a T-Guard infusion reaction. All other sample aliquots will be PK tested at Ardena. Remaining PK samples may be selected for free-RTA + free-mAb testing.
All Study Participants	Peripheral Blood (SST Clot Tube) 5 mL Serum GVHD Biomarkers REG3α and ST2	Pre-treatment initiation Day 0 Post-treatment initiation Day 6 (just prior to 4 th infusion for T-Guard arm) Days 14 and 28	Collect the blood sample and place 5 mL SST Vacutainer tube containing clot activator. Allow blood samples to clot upright for 30-60 minutes in a tube rack prior to centrifugation. In Europe: Samples should be aliquoted and stored at -80°C.	US: Centrifuged blood sample tube will be shipped at 2-8°C on the day of collection, to the BMT CTN Biorepository and stored at -80°C. Serum aliquots will be batch-shipped to [name] lab at Mt. Sinai for analysis. Europe: Frozen serum aliquots will be batched-shipped to Ardena, and forwarded [name] lab in Regensburg, Germany for analysis.

Subjects	Sample Type	Sample Collection Time Points	Sample Collection and Sample Processing Summary	Shipping Specifications

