All Study Participants	Urine 6 mL GVHD Related 3IS Biomarkers	Pre-treatment initiation Day 0 Post-treatment initiation Day 6 (just prior to 4 th infusion for T-Guard arm) Days 14 and 28	In the US: Place urine in sterile transport tube for same-day shipping. In Europe: Aliquote urine and place in ultra-freezer temperature cryovials and stored at -80°C.	US: Urine sample tube will be shipped at 2-8°C on the day of collection to the BMT CTN Biorepository, aliquoted, and stored at -80°C. Europe: Frozen aliquots will be periodically batched-shipped to Ardena, and forwarded to [name] lab in Regensburg, Germany for analysis.
50 Study Participants in selected centers (25 on T-Guard and 25 on ruxolitinib)	Peripheral Blood (Sodium Heparin Vacutainer Tubes) 30 mL Peripheral blood mononuclear cells (PBMC) viably frozen	Pre-treatment initiation Day 0 Post-treatment initiation Days 14, 28, 56, and 180	Collect the blood sample and place 10 mL into each of three Vacutainer tubes containing sodium heparin anticoagulant. Gently mix sample by inversion 8-10 times to mix sample well with anticoagulant. In Europe: Samples will be viably frozen at site.	US: Blood sample tubes will be shipped at 2-8°C on the day of collection, to the BMT CTN Biorepository for viably freezing. Europe: Samples should be viably frozen at site and batch-shipped to Ardena. Samples will be banked for later analysis (e.g. CMV/EBV Alloreactive T-Cells).
50 Study Participants in selected centers (25 on T-Guard and 25 on ruxolitinib)	Peripheral Blood (Cyto-Chex BCT) 10 mL Flow Cytometry Immune Profiling	Pre-treatment initiation Day 0 Post-treatment initiation Days 14, 28, 56, and 180	Collect the blood sample and place 5 mL into each of two Cyto-Chex tubes containing EDTA anticoagulant and cell fixative. Gently mix sample by inversion 8-10 times to mix sample well with anticoagulant and cell fixative reagent.	Cyto-Chex blood tubes will be shipped at 2-8°C on the day of collection to the RPCI project laboratory (US) or Ardena (Europe).

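### The exploratory biomarker-risk model for Day 28 CR adjusts only for arm, although the biomarker assay laboratory and handling differ by region

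*Combined protocol and SAP*

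**What the plan says.** Sections 3.5.1.5 and 5.8.5 define a biomarker risk score. Serum ST2 and REG3α and urine 3-IS "will be used to estimate the probability of NRM at Day 180 post-assessment for each participant, using the NRM risk model from" a cited publication; section 5.8.5 likewise says that the serum markers "and the 3-IS urine levels at enrollment and Day 6, 14, and 28 post-randomization will be used to estimate NRM probabilities". A participant is high risk when the estimated NRM exceeds 0.29, with one threshold for everyone. High-risk proportions are reported by arm at each time point, and Day 28 CR is described by enrollment risk group within arm. A logistic model then evaluates the "prognostic value of biomarker risk (high vs. not) on the chance of attaining a Day 28 CR while adjusting for treatment arm". No other covariate is named.

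The sample table in Appendix B treats the two regions differently.

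- **US serum (REG3α, ST2).** The centrifuged tube travels at 2-8°C on the day of collection to the central biorepository and is stored there at -80°C. Then: "Serum aliquots will be batch-shipped to [name] lab at Mt. Sinai for analysis".
- **European serum.** Aliquots are made and stored at -80°C. Then: "Frozen serum aliquots will be batched-shipped to Ardena, and forwarded [name] lab in Regensburg, Germany for analysis".
- **US urine (3-IS).** "US: Urine sample tube will be shipped at 2-8°C on the day of collection to the BMT CTN Biorepository, aliquoted, and stored at -80°C". The entry ends there.
- **European urine.** "Frozen aliquots will be periodically batched-shipped to Ardena, and forwarded to [name] lab in Regensburg, Germany for analysis".

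No bridging, calibration or common assay is described for these markers. Section 5.1.2 makes region (US vs. Europe) a randomization stratum, and section 5.5 includes region, age group and aGVHD grade in the primary CR model.

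**The concern.** A prognostic odds ratio is meant to say whether participants classed as high risk have a different chance of CR. Here the classification comes from one laboratory and handling route for every US participant and from another for every European participant, both judged against the same absolute cut-off. Any systematic difference between the two routes moves a whole region's participants across 0.29. If CR rates also differ by region, for reasons such as case mix or supportive care, a model without region credits that difference to the biomarker.

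Two reported results are exposed: the prognostic odds ratio, and the high-risk proportions pooled over regions. Sampling noise aside, the treatment comparison is not exposed.

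**Working it through.** The plan states no sample size, power or expected odds ratio for this analysis, so there is no figure of its own to reproduce. The check has two parts.

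**1. Passages side by side.** Score inputs and threshold: sections 3.5.1.5 and 5.8.5, the same for all participants. Assay route: Appendix B, split by region for serum and urine. Model: section 5.8.5, arm only. Region is recorded for everyone (section 5.1.2) and used in the primary CR model (section 5.5). Laboratory and handling therefore coincide with region, and the model contains nothing that absorbs a regional difference.

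**2. Size, by illustration.** Inputs:

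- Share high risk without any offset: 11/20 = 55%, from section 1.3.1.2.2 ("A validated two biomarker algorithm classified the majority of patients (11/20) as high-risk"). It is used only as a plausible level.
- Assumed: half the participants in each region; score distributed N(0,1) within region; laboratory offset of 0.25 or 0.5 SD in one region; regional CR rates of 30% and 40%, or 25% and 45%.
- No true association between risk group and CR within either region (odds ratio 1.00).

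Share high risk in the offset region = Φ(Φ⁻¹(0.55) + offset). This gives 64.6% for 0.25 SD and 73.4% for 0.5 SD. The pooled high-risk share moves from 55% to (55 + 64.6)/2 = 59.8% or (55 + 73.4)/2 = 64.2%.

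Pooled 2×2 cells for the smallest case (0.25 SD; CR 30% without the offset, 40% with it):

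- High risk, CR: 0.5 × (0.55 × 0.30 + 0.646 × 0.40) = 0.2118
- High risk, no CR: 0.5 × (0.55 × 0.70 + 0.646 × 0.60) = 0.3864
- Not high risk, CR: 0.5 × (0.45 × 0.30 + 0.354 × 0.40) = 0.1382
- Not high risk, no CR: 0.5 × (0.45 × 0.70 + 0.354 × 0.60) = 0.2636

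Odds ratio = (0.2118 × 0.2636)/(0.3864 × 0.1382) = 1.045.

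| Offset | High risk in the two regions | OR, CR 30%/40% | OR, CR 25%/45% |
|---|---|---|---|
| 0.25 SD | 55% / 64.6% | 1.045 | 1.092 |
| 0.5 SD | 55% / 73.4% | 1.092 | 1.194 |

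If the offset region has the lower CR rate, the values are the reciprocals, 0.96 down to 0.84.

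A second set of assumptions gives a similar picture. Centre the high-risk share at 55% and CR at 34.5%, the mean of the 43% and 26% in section 5.1.5. Regional gaps of 10 to 30 points in high-risk share and 5 to 15 points in CR, Europe lower, give 0.98 to 0.82 for a true 1.00. With gaps of 30 and 15 points and the CR gap reversed, the result is 1.22. For a true odds ratio of 0.50, the pooled value runs from 0.44 to 0.67 over the combinations tried. With a true odds ratio of 1.00 and either gap at zero, the pooled value is exactly 1.00.

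**Against sampling error.** With all 246 participants and the cells above, the standard error of the log odds ratio, √(Σ 1/(246 × cell)), is 0.27 to 0.28. The 95% interval thus spans a factor of about 1.7 either way. The biases in the table are log(1.045)/0.273 = 0.16 to log(1.194)/0.281 = 0.63 standard errors.

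**The case against.** The strongest reply is that this is an exploratory prognostic model with no alpha or decision attached, that no document shows the two laboratories to differ, and that the illustrated bias is well inside sampling error. Its closest sibling, the EASIX prognostic analysis in section 5.8.8, also omits region, age and grade, so adjusting only for arm fits the plan's exploratory tier. US serum is centrifuged before a same-day shipment, which narrows the handling contrast. All of this stands, and it sets the severity. It does not remove the point: here the exposure itself is measured by region-specific routes, a split that the plan does not describe for EASIX.

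A reader might infer three stronger claims that the documents do not support.

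- **That the score cannot be computed for US participants.** The Appendix B table is silent about a US 3-IS assay; it does not rule one out. The same appendix lists urine biomarker evaluation among the planned studies and leaves shipping detail to a Research Sample Information Guide that is not supplied. What holds is that the protocol states no route to a 3-IS result for US urine.
- **That 3-IS does not belong in the score.** The two-marker algorithm in section 1.3.1.2.2 describes the Phase 1/2 study and is not linked to the risk model cited in section 5.8.5, whose equation the documents do not give.
- **That a single laboratory or a split-sample bridging study is required.** Either would help, but both need extra resources, and no documented laboratory difference demands them.

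Age group and aGVHD grade are also not needed for this mechanism. Adding grade would change the question to prognostic value beyond grade.

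**Conclusion.** The point holds as a minor one. In section 5.8.5 the exposure measurement is fully confounded with region, and the logistic model leaves region out. Bias in the odds ratio under no true effect needs both a laboratory offset and a regional CR difference. Under the assumed offsets and CR gaps, a true odds ratio of 1.00 would appear as about 1.05 to 1.19 (or the reciprocals). The pooled high-risk share would rise by about 5 to 9 points from a laboratory offset alone. The offset, the regional CR rates and the equal regional split are all assumptions.

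A reader might go on to infer that the comparison of T-Guard with ruxolitinib is distorted. The documents point the other way: randomization is stratified by region, so a laboratory difference should fall equally on both arms, and high-risk proportions and CR by risk group are reported within arm. The primary test, alpha and sample size do not depend on this analysis.

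**What to change.** In section 5.8.5, add region (US vs. Europe) to the logistic model alongside treatment arm, and tabulate high-risk proportions by region within arm at each time point. Age group and aGVHD grade are optional.

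The cost is one model term and one split of a planned table. Region is already collected as a stratification factor. Adjustment removes the confounding by region from the odds ratio. It does not correct participants misclassified at 0.29 by a laboratory offset, but the regional table would show whether the high-risk shares differ enough to question the common cut-off.

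Two clarifications belong in the same revision and need only wording: state in sections 3.5.1.5 and 5.8.5 which analytes enter the NRM score, and name the laboratory that will assay US urine for 3-IS in Appendix B. Both are best settled before biomarker results are seen, so that the score definition is not chosen afterwards.
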